6.2.1 Inclusion Criteria

An adult patient (18 years of age or older) with CD for whom Humira therapy is indicated according to the local product label and who meet the following criteria may be enrolled in this study:

1. Patients to be enrolled must fall into one of the following categories:
 - Patients who are newly prescribed Humira therapy (have never been treated with adalimumab).
 - Patients who are current participants in AbbVie sponsored investigational CD trials, are currently receiving Humira and for whom the treating physician has made the decision to continue with Humira therapy beyond the duration of the investigational trial.
 - Patients who were prior participants in AbbVie sponsored investigational Crohn's disease trials, who have not had dose interruptions since the last dose of registry drug, where the Investigator can provide source documentation of dosing information.
 - Patients who are currently receiving Humira, as per the local product label, who have not had dose interruptions since the induction dose of Humira where the Investigator can provide source documentation of dosing information.
2. Patients willing to consent to data being collected and provided to AbbVie.
3. Patients capable of and willing to give written informed consent and to comply with the requirements of the Registry protocol.

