6.4.8 Adalimumab Treatment and Dosing Changes

The participating physician will provide the patient a prescription for HUMIRA, along with instructions for appropriate use. At subsequent protocol-defined study visits the physician will collect the start and stop dates, any dose interruptions and reason for the dose interruption that may have occurred since the last study visit. The dose, dates of administration, any dose interruptions and the reason for the interruption will be captured in the source documents and eCRFs.

Dose interruptions for the study will be defined as patients missing > 1 dose. The reason(s) for interruptions will be captured on the eCRF.

Most clinical data associated with this study will be collected and reported electronically (eCRF) via a web address and secure password. Patient questionnaires will be completed on forms formatted for fax scanning. The site will fax or email completed forms into the designated Study Help Desk.

At the enrollment visit, the physician will complete the Enrollment eCRFs by obtaining and recording all available required information, including visit date, demographic data, concomitant diseases and concomitant medications.

At subsequent visits corresponding to the schedule of assessments ([Table 1](#)), the physician will complete the appropriate eCRF by obtaining and recording all available information. Since this is an observational study conforming to usual clinical practice, data from subject visits that most closely correspond to the schedule of assessment at Months 3, 6, 9, 12, 18, 24, 30, 36, 42, 48, 54, 60 66 and 72 will be accepted. For example, if a patient visits the physician's site at Month 5, this is close to the protocol-defined 6-month study

visit, so data can be collected for this visit. If the same patient unexpectedly returns for a visit to the physician's site at a date closer to the 6-month visit, no further PRO data needs to be collected since the data was previously collected. Safety data that meets the criteria for collection should be collected regardless of protocol-defined study visits.

If a patient completes the 6-year observation period study completion of eCRFs should be completed.

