10.0 Statistical Methods and Determination of Sample Size

10.1 Statistical and Analytical Plans

Analyzable Populations:

Safety Populations During the Registry:

The Registry Safety Population consists of all patients who received at least one dose of Humira (adalimumab) in the Registry. This will be the population for safety analyses in the Registry and include safety data collected during the Registry only.

The "Episodic Dosing" Population will consist of patients in the Registry Safety Population who:

- discontinue Humira (adalimumab) at least once for more than 70 days and receive at least one dose of adalimumab after the treatment interruption,
- do not receive any other biologics during the treatment interruption and,
- provide data before and after Humira (adalimumab) treatment interruption period(s)
- and include safety data collected during the Registry only.

For patients previously treated with commercial Humira before enrollment into the Registry, Day 1 of adalimumab treatment will be the 1st day of Humira therapy, i.e., before enrollment into the Registry. Detailed information on concomitant medications, safety and effectiveness between the 1st dose of Humir and enrollment into the Registry will be available for these patients.

Re-enrollment Safety Population:

The Re-enrollment Safety Population consists of all patients who were discontinued from the Registry due to prior protocol withdrawal criteria (i.e., patients who have discontinued Humira therapy) or discontinued for other reasons and re-consent to participation in the Registry. This will be the population for safety analyses of data collected during the re-enrollment period.

For patients that re-enroll in the Registry, safety information collected between registry discontinuation and re-enrollment based on a retrospective review of their patient records will be analyzed separately.

HCP Safety Population:

The HCP Safety Population consists of all patients that decline re-enrollment to participation in the Registry or who have discontinued from the Registry for other reasons and consent to data release for the completion of a simplified HCP questionnaire in the direct to HCP process. This will be the population for safety analyses of data collected on HCP questionnaire.

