10.5 Safety Analyses

For the Registry Safety Population, treatment-emergent SAEs and adverse events of interest will be summarized. Treatment-emergent SAEs and adverse events of interest are defined as: (1) new events that begin either on or after the first dose of Humira through the last dose of Humira plus 70 days; or (2) increase in severity of ongoing SAEs that had occurred before the first dose date of Humira. The number and percent of patients experiencing SAEs and adverse events of interest will be tabulated by body system and Medical Dictionary for Drug Regulatory Activities (MedDRA[®]) preferred term. The percent of patients will be presented with 95% confidence intervals. In addition, summary of SAEs and adverse events of interest by severity and relationship to registry drug will be presented.

The event rate of SAEs and of each adverse event of interest per 100 patient year of observation will be presented. Event rates will be presented with 95% confidence intervals. For patients enrolled from a prior CD study, the total number of SAEs and adverse events of interest will include the events reported during their participation in the previous study plus any events reports during the Registry.

In addition, Observational AEs: SAEs and AEs of interest occurring from the first dose of Humira in the registry through the last contact including re-enrollment period and during the HCP process will be tabulated.

For the 'Episodic Dosing' Population, following analyses will be provided:

- Summary of SAEs and AEs of special interest will be provided for patients with episodic dosing and without episodic dosing.

- Summary of SAEs and AEs of special interest will be provided before the treatment interruption and after the treatment interruption for patients with episodic dosing.
- For each SAE and AE of special interest, and each episodic dosing, a shift table to summarize number and percentage of patients who have the event or not before the treatment interruption and after the treatment interruption.

For the Re-enrollment Safety Population, the number and percent of patients experiencing SAEs and AEs of interest during the re-enrollment period will be tabulated by body system and MedDRA preferred term. In addition, the number and percent of patients experiencing SAEs and AEs of interest collected between registry discontinuation and re-enrollment based on a retrospective review of their patient records will be tabulated separately.

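### Section 10.5 gives one pooled event rate for new Humira starters and patients already on Humira, which understates the new-starter rate for any event that clusters early

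*Protocol*

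**What the plan says.** Section 6.2.1 lists four entry categories:

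1. Patients newly prescribed Humira who have never received adalimumab.
2. Current participants in sponsor trials "for whom the treating physician has made the decision to continue with Humira therapy beyond the duration of the investigational trial".
3. Former trial participants "who have not had dose interruptions since the last dose of registry drug".
4. Commercial users: "Patients who are currently receiving Humira, as per the local product label, who have not had dose interruptions since the induction dose of Humira", with source documentation of dosing.

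Section 6.4.8 defines the term: "Dose interruptions for the study will be defined as patients missing > 1 dose".

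Section 10.1 combines all four: "The Registry Safety Population consists of all patients who received at least one dose of Humira (adalimumab) in the Registry". It restricts this population to safety data from the Registry. Section 10.2 makes it the default for every analysis. Section 10.5 then states: "The event rate of SAEs and of each adverse event of interest per 100 patient year of observation will be presented", with 95% confidence intervals. The separate safety summaries in 10.5 are for episodic dosing, re-enrollment and the HCP process; none is by new versus established use. Section 10.3 names prior therapies and exposure duration among covariates whose influence on the endpoints will be assessed, without tying them to the rates.

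Two further statements affect what is counted. Section 10.1 sets Day 1 for prior commercial users at their first dose, before enrollment. Section 10.5 adds events from the previous study for patients who come from a prior Crohn's disease trial.

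**The concern.** A rate per patient-year summarizes the population well when risk is roughly constant over time on drug. Several events of interest here need not behave that way: serious allergic reactions, serious infections, and events that lead to stopping Humira. New starters contribute their first months on drug to the Registry. Established users contribute mainly later time.

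Category 4 adds selection to this mixing. Events leading to premature discontinuation are themselves events of interest under section 7.1.2. A commercial user who stopped for such an event soon after induction is barred from that category, so those enrolled have been selected for tolerance. Starting the clock at enrollment does not remove this.

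At stake is the interpretation of the registry's primary results. The pooled rate depends on the recruitment mix of new and established users, and it can be read as the risk of starting Humira when it is not.

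**Working it through.** **Plan figures reproduced.** Section 10.7 uses a median time to dropout of 3 years, so λ = ln 2 / 3 = 0.231. Patient-years per patient over 6 years are (1 − e^(−6λ))/λ = 0.75/0.23105 = 3.246, and 5,000 × 3.246 = 16,230. This agrees with the protocol. The lymphoma calculation also reproduces: 15,180 patient-years and 17 events give a one-sided type I error of 0.0499 and power of 0.904. This point does not touch it.

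**Inputs for the pooling check.**
- From section 10.7: λ = 0.231 and 3.246 patient-years, applied to both groups, so the share of patients equals the share of person-time.
- Assumed, because the protocol gives no value: established-user share f of 25%, 50% or 75%; early hazard k times the later one, k = 2, 3 or 5; an early window of 6 months.
- Also assumed: established users enter after that window, and only events and time from enrollment count.

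**Early share of a new starter's time.** s = [(1 − e^(−0.231 × 0.5))/0.231] / 3.246 = 0.472/3.246 = 0.1455.

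**Rates, with the later hazard set to 1.**
- New starters, whole follow-up: N = 1 + s(k − 1). This is 1.1455, 1.291 and 1.582 for k = 2, 3 and 5.
- Pooled: P = 1 + (1 − f)s(k − 1).
- Shortfall: 1 − P/N = f·s(k − 1)/[1 + s(k − 1)].

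| k | f = 25% | f = 50% | f = 75% |
|---|---|---|---|
| 2 | 3.2% | 6.4% | 9.5% |
| 3 | 5.6% | 11.3% | 16.9% |
| 5 | 9.2% | 18.4% | 27.6% |

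Example: k = 3 and f = 50% give P = 1 + 0.5 × 0.1455 × 2 = 1.1455, and 1.1455/1.291 = 0.887.

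**Within the first 6 months after enrollment.** The pooled rate is (1 − f)k + f. At k = 3 and f = 50% this is 2.0 against 3.0 in new starters, or 33% lower.

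**Separating pooling from averaging over time.** Against the first-6-month rate, the pooled rate is 62% lower at k = 3 and f = 50% (1.1455/3 = 0.382), and 74% lower at k = 5 (1.291/5 = 0.258). With no established users at all, the gaps are already 57% (1.291/3 = 0.430) and 68% (1.582/5 = 0.316). Pooling adds only 5 to 6 percentage points; the rest comes from using one rate for up to six years.

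**The case against.** The strongest reply is that stratified tables usually belong in the SAP, which is not at hand, and that 10.5 does not forbid them. Section 10.3 already commits to examining prior therapies, which under 6.4.5 include commercial Humira, and exposure duration. This is real partial mitigation. But 10.5 itself chooses its safety breakdowns, and new versus established use is not among them.

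A second reply is that the objective is long-term safety and the registry is sized on lymphoma, so a rate over all label-treated patients fits. That supports keeping the pooled rate. It does not support leaving it as the only rate for every event of interest, including those likely to occur early.

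Several stronger readings are tempting but unsupported:
- *All established users are selected for uninterrupted use since induction.* Only category 4 carries that condition. Category 2 has no interruption condition, and category 3's runs from the last dose of the earlier drug supply.
- *All established users are past the early period.* Category 4 sets no minimum prior duration, so a patient just past induction may still contribute early time. The shortfall is then smaller than in the table.
- *Pooling hides 62-74% of the early rate.* Most of that gap is averaging over six years.
- *Roll-over patients contribute no early events.* Section 10.5 adds their prior-study events. It does not state the matching patient-years, and the addition is in tension with the Registry-data restriction in 10.1.

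**Conclusion.** The point holds in a limited form. The protocol fixes one pooled rate per 100 patient-years for never-treated starters and prior users, and one prior-user category excludes patients whose treatment was interrupted early. For events that cluster soon after starting, that rate understates the rate in new starters, by about 3-28% over whole follow-up and 11% at a 50% share with a threefold early hazard.

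These sizes illustrate and do not estimate. They rest on an assumed established-user share, hazard ratio and 6-month window, on equal attrition, on established users being past the window, and on counting from enrollment. The 28% is the extreme corner of the grid. The downward direction itself depends on higher early hazard: with constant hazard (k = 1) the shortfall is zero, and for long-latency events there is no reason to expect it. A reader should not infer that the sample size or the lymphoma calculation is wrong, or that the bias is established for every event. For trial roll-overs the effect cannot be signed until 10.1 and 10.5 agree on which events and person-time count.

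**What to change.** Keep the pooled rate, and add to section 10.5:

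- Each SAE and event-of-interest rate separately for category 1 and for categories 2-4.
- The same rates by time since first Humira dose, for example 0-6, >6-24 and >24 months. Prior users enter the risk set at enrollment, and only events and person-time from enrollment are counted.
- A statement that category 1 is the main cohort for early-onset events.
- Reconciliation of the Registry-data restriction in 10.1 with the addition of prior-study events in 10.5. If prior-study events are kept in any rate, state the matching patient-years.

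No new data collection or change in sample size is needed. Prior commercial Humira (6.4.5), treatment dates (6.4.8) and the previous-study subject number (6.4.2) are already captured. The cost is extra tables and wider intervals within strata. A stratum with half the events has a standard error on the log-rate scale √2 = 1.41 times that of the pooled rate, so rare events will be imprecise in each stratum and should still be read alongside the pooled figure.

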7.4 Adverse Event Collection Period

Serious adverse events and adverse events of interest will be reported to AbbVie from the time the physician obtains the subject's initial authorization to use and disclose information (or the subject's informed consent) throughout the patient's participation in the Registry, or direct to HCP process, and/or until 70 days following discontinuation of Humira administration have elapsed (whichever period is longer). A medical event that occurs after a patient discontinues the registry that is considered to be related to the patient's exposure to Humira will be reported via standard post-marketing reporting practices.

In the event Humira therapy is interrupted, SAEs and adverse events of interest will be collected throughout the interruption. If treatment with adalimumab is permanently discontinued for any reason, the reason will be recorded and the patients should be encouraged to remain in the registry for the full 6 years so important safety information can be obtained.

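### Sections 10.1 and 10.5 set incompatible event counts for the main safety rates, and the start of the patient-year denominator is not stated, so the rates can be biased in either direction

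*Protocol*

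**What the plan says.** Four statements in the protocol bear on which events and which time enter the safety rates.

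- **Population (10.1).** Of the Registry Safety Population: "This will be the population for safety analyses in the Registry and include safety data collected during the Registry only".
- **Event count (10.5).** For patients coming from an earlier Crohn's disease study, "the total number of SAEs and adverse events of interest will include the events reported during their participation in the previous study", together with their Registry events. This follows directly on the rate statement, "The event rate of SAEs and of each adverse event of interest per 100 patient year of observation will be presented".
- **Time window (10.1 and 10.5).** Treatment-emergent events include "new events that begin either on or after the first dose of Humira through the last dose of Humira plus 70 days", with no restriction to doses taken in the Registry. For users of commercial Humira, "Day 1 of adalimumab treatment will be the 1st day of Humira therapy, i.e., before enrollment into the Registry". By contrast, the Observational AEs in 10.5 are those "occurring from the first dose of Humira in the registry through the last contact".
- **Event capture (10.1, 6.3.1 and 7.4).** Section 10.1 says that detailed safety information between first dose and enrollment will exist for commercial users. Sections 6.3.1 and 7.4 start collection later: serious adverse events and events of interest "will be reported to AbbVie from the time the physician obtains" the patient's authorization or consent.

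The entry criteria in 6.2.1 matter too. Apart from new users, they admit current trial participants still on Humira, former trial participants without an interruption since their last dose, and current commercial users "who have not had dose interruptions since the induction dose of Humira". Section 6.4.8 defines an interruption as more than one missed dose.

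**The concern.** The primary objective is long-term safety, and section 10.7 sizes the Registry to exclude a doubling of the lymphoma rate. A rate is interpretable only if its events and its patient-years cover the same period. Here the protocol gives two rules for the events and no starting point for the patient-years. Patients treated before enrollment may therefore contribute earlier events without the matching time, or earlier time without a fair chance of showing the event. The first raises the rate. The second lowers it for events that would have kept a patient out of the Registry, and a lowered rate makes it easier to declare a doubling excluded when it is not. Section 10.6 plans periodic cumulative analyses, so a mismatch would recur in each report.

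**Working it through.** **1. The plan's own figures (10.7) reproduce.**
- Background rate: 0.73 × 0.1052 + 0.27 × 0.0263 = 0.0839 per 100 patient-years (PY), stated as 0.084. Doubled: p0 = 0.168.
- A doubling is excluded after x events in n PY if χ²(0.95; 2(x+1)) / (2n) < p0. The smallest workable count is x = 17, needing n of at least 15,178 PY (stated 15,180). At 15,180 PY the one-sided error is 0.0499 and the power 0.904.
- Exposure per patient: (1 − e^(−0.231×6)) / 0.231 = 3.246 PY; × 5,000 = 16,230 PY. The integral runs from 0 to 6 years and contains no pre-enrollment time, so the sample size calculation is unaffected.

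**2. The two event rules side by side.** For a roll-over patient with a serious event in the earlier study, 10.1 leaves the event out and the added sentence in 10.5 puts it in. The treatment-emergent definition adds a second route back in time for anyone whose first dose preceded enrollment. That 10.5 specifies the first dose in the Registry for Observational AEs, but not for treatment-emergent events, shows that the start points differ within one section.

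**3. The denominator.** The only description is patient-years of observation. Both readings need to be followed through.

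*Reading A: earlier events counted, their PY not.* If a share f of all relevant PY is left out and the event rate is equal in both periods, the rate is multiplied by 1/(1 − f).

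| f (assumed) | Factor |
|---|---|
| 10% | 1.11 |
| 20% | 1.25 |
| 30% | 1.43 |

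*Reading B: pre-enrollment PY counted.* A patient who died, or whose event ended Humira, before enrollment could not enter by the already-treated routes in 6.2.1. For such events the earlier time is event-free by selection. Assume lymphoma is such an event and the true rate is 0.168 per 100 PY. The 16,230 Registry PY then yield 16,230 × 0.00168 = 27.27 expected events, and the added PY yield none. The critical count c is the largest x meeting the rule in step 1 at the enlarged total; the error is P(X ≤ c) for a Poisson mean of 27.27.

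| Added PY (assumed) | Total PY | Dilution = added/total | Apparent rate per 100 PY | c | Chance of wrongly excluding a doubling |
|---|---|---|---|---|---|
| 0 | 16,230 | 0% | 0.168 | 18 | 4.0% |
| 1,000 | 17,230 | 5.8% | 0.158 | 19 | 6.3% |
| 1,500 | 17,730 | 8.5% | 0.154 | 20 | 9.3% |
| 2,500 | 18,730 | 13.3% | 0.146 | 22 | 18.2% |

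For scale, 1,000 PY would be 20% of 5,000 patients with one earlier year each, and 2,500 PY would be 50% with one year each. The protocol gives neither the share nor the duration.

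**4. Event capture.** Section 7.7 sets out retrospective event collection for patients who re-enroll. For commercial users before consent, 6.4.5 provides for concomitant medication changes, and 6.3.1 and 7.4 begin event reporting at consent. The assurance in 10.1 that safety information will be available for that period therefore has no matching collection rule.

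**The case against.** A reader might infer that event-free, or immortal, pre-enrollment time does enter the lymphoma and serious-event rates and pulls them down. The documents do not support that. Nothing places pre-enrollment time in the denominator; the Day 1 sentence in 10.1 dates treatment and does not define person-time; and the 16,230 PY in 10.7 exclude such time. Taken alone, the added sentence in 10.5 raises rates, which is conservative for excluding a doubling. This stands, and it makes the direction of bias conditional.

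The selection argument also has limits. A serious event without an interruption of more than one dose does not bar entry. Current trial participants face no interruption condition, and former participants face one only from their last dose onward. The sole exclusion in 6.2.2 concerns treatment outside the local label and names no prior malignancy. Reading B is therefore confined to fatal or treatment-ending events. That lymphoma is one of these is plausible, but the protocol does not say so.

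Nor can one say that commercial users' pre-enrollment events go wholly uncaptured, since 10.1 says otherwise. What remains is a conflict between 10.1 and sections 6.3.1 and 7.4.

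Finally, the one-sided 5% rule comes from sample sizing, whereas 10.5 plans 95% confidence intervals without a test. Exact person-time rules often sit in a statistical analysis plan, which is not shown here, and Observational AEs already give a registry-start count, though not a rate. These points temper the size of the problem. They do not reconcile two rules that the protocol itself has fixed.

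**Conclusion.** The point holds as a contradiction. The protocol states two incompatible event counts for its primary safety rates, lets the treatment-emergent window open before enrollment for already-treated patients, and leaves the start of the denominator open. It also promises pre-enrollment safety information for commercial users while collecting events only from consent.

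The bias is conditional. Under reading A the inflation is 1.11 to 1.43, given 10-30% of PY omitted and equal rates in both periods. Under reading B the error of excluding a doubling goes from 4% to 6-18%, given 1,000-2,500 added event-free PY, lymphoma acting as a bar to entry, and the decision rule of 10.7 being applied. Larger added exposures, such as 5,000 or 7,500 PY, would give 38% and 68%, but they need still higher shares and durations of prior treatment that the protocol does not supply and should not be read as an estimate. Reading B does not extend to serious adverse events in general.

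**What to change.** - Reconcile 10.1 and 10.5 by taking previous-study events out of the main Registry rates.
- State in 10.5 that, for every patient, the event count and the person-time for these rates both begin at the later of registry consent and first registry dose. Already-treated patients then enter by delayed entry, and time since first Humira dose can be kept as a descriptive variable.
- If an all-exposure or prior-study rate is wanted, show it in a separate table with matching events and patient-years.
- Reconcile 10.1 with 6.3.1 and 7.4 on whether, and how, events between first commercial dose and consent are captured.

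For the main Registry rates this takes wording and an analysis start date, with no new data. The price is fewer events and patient-years in the headline rate than an all-exposure rate would have.
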